7.2 Anticipated Adverse Event

Any undesirable clinical occurrence in a subject that may be expected to occur during routine care. These will not be reported unless thought to be study related.

Anticipated adverse events may include but are not limited to:

- Reflux
- Wind
- Nappy rash
- Crying

7.3 Serious Adverse Events

Serious Adverse Event (SAE) or **Serious Adverse Device Event (SADE)** any adverse medical or occurrence that:

1. Led to a death.
2. Led to a serious deterioration in health of a subject that:
 - Resulted in a life-threatening illness or injury.
 - Resulted in a permanent impairment of body function or permanent damage to a body structure.
 - Resulted in an increased length of existing hospitalisation.
 - Resulted in requiring medical or surgical intervention to prevent permanent impairment of a body structure or a body function.
3. Might have led to death or a serious deterioration in health had suitable action or intervention not taken place.

7.4 Reporting of Adverse Events

All SAEs / SADEs must be reported by the Investigator to the Sponsor within 24 hours of learning of the incident, by the completion and emailing of an SAE report form, a copy of which will be available in the ISF. Notification of the SAE should be made by phone/email, then the SAE form emailed even if not entirely complete, within the 24-hour period of awareness.

The Sponsor will then liaise with the Chief Investigator and report the SAE to the REC, and the NHS Trust Risk reporting mechanisms (Datix). If deemed possibly device related, it will also be reported to the MHRA and the other PIs and SIs involved in the study.

All adverse events including AEs, ADEs, SAEs and SADEs which occur during the participation in the clinical study must also be recorded in the patient's notes and on the Adverse Event log within 10 working days and will be tracked by the Sponsor representative through regular site monitoring.

Severity of AEs must be identified. Table 2 provides definitions to be used to assess AEs.

TABLE 2: DEFINITIONS OF SEVERITY FOR ADVERSE EVENTS

Mild:	Symptom is only slightly noticeable to the subject or does not cause discomfort; does not negatively influence functioning; prescription drugs not required for relief of symptom but may be prescribed.
Moderate:	Symptom is of a sufficient severity to cause discomfort; performance of daily activities is negatively influenced; treatment for symptom may be needed.
Severe:	Symptom causes severe discomfort and incapacitation having significant impact on the subject's performance of daily activities; treatment for symptom may be given and/or subject's hospitalization may be extended.
Life Threatening:	An event that places the subject at immediate risk of death from the event.
Fatal:	An event that was the direct cause of the subject's death.

“Severe”, “Life-Threatening” or “Fatal” AEs that are determined to be “causally related” to the procedure are to be reported to the Sponsor within 24 hours of the site's knowledge of the event (See definition in Table 3).

TABLE 3: DEFINITIONS OF RELATIONSHIP OF ADVERSE EVENTS

Not related:	Relationship to the device, comparator or procedures can be excluded when: 
 the event has no temporal relationship with the use of the investigational device, or the procedures related to application of the investigational device the serious adverse event does not follow a known response pattern to the medical device (if the response
---------------------	---

	
pattern is previously known) and is biologically implausible;
 
 • the discontinuation of medical device application or the reduction of the level of activation/exposure - when clinically feasible – and reintroduction of its use (or increase of the level of activation/exposure), do not impact on the serious adverse event; • the event involves a body-site or an organ that cannot be affected by the device or procedure; • the serious adverse event can be attributed to another cause (e.g. an underlying or concurrent illness/ clinical condition, an effect of another device, drug, treatment or other risk factors); • the event does not depend on a false result given by the investigational device used for diagnosis⁹, when applicable; 
In order to establish the non-relatedness, not all the criteria listed above might be met at the same time, depending on the type of device/procedures and the serious adverse event.

Possible:
	
The relationship with the use of the investigational device or comparator, or the relationship with procedures, is weak but cannot be ruled out completely. Alternative causes are also possible (e.g. an underlying or concurrent illness/ clinical condition or/and an effect of another device, drug or treatment). Cases where relatedness cannot be assessed, or no information has been obtained should also be classified as possible.

Probable:
	
The relationship with the use of the investigational device or comparator, or the relationship with procedures, seems relevant and/or the event cannot be reasonably explained by another cause.


Causal Relationship:
	
The serious adverse event is associated with the investigational device, comparator or with procedures beyond reasonable doubt when:
 
 • the event is a known side effect of the product category the device belongs to or of similar devices and procedures; • the event has a temporal relationship with investigational device use/application or procedures; • the event involves a body-site or organ that 
 ○ the investigational device or procedures are applied to ○ the investigational device or procedures have an effect on;

	
• the serious adverse event follows a known response pattern to the medical device (if the response pattern is previously known);• the discontinuation of medical device application (or reduction of the level of activation/exposure) and reintroduction of its use (or increase of the level of activation/exposure), impact on the serious adverse event (when clinically feasible);• other possible causes (e.g. an underlying or concurrent illness/ clinical condition or/and an effect of another device, drug or treatment) have been adequately ruled out;• harm to the subject is due to error in use;• the event depends on a false result given by the investigational device used for diagnosis, when applicable; 
In order to establish the relatedness, not all the criteria listed above might be met at the same time, depending on the type of device/procedures and the serious adverse event.

--	--

8. STATISTICS AND DATA ANALYSIS

The primary endpoint is babies' truncal skin surface temperature variation; also termed core or central temperature. This is expected to fluctuate but remain within normal temperature limits (36.5 to 37.5 degrees Celsius). Variations from this endpoint will be analysed and compared statistically between the two arms of the study.

Thirty-six completed datasets are required for the analysis to be valid. A complete subject dataset will be deemed acceptable if 19 of the 24, once-hourly temperature observations have been recorded for each incubator type (*i.e.* 79% compliance). This degree of compliance was considered acceptable for analysis because it is still greater than the routine standard for this type of incubator care for clinically stable infants of 30 weeks GA or greater, which is often every three hours. Although data analysis will be largely descriptive, the performance of the mOm incubator will be statistically quantified by assessment of the fluctuations of babies' temperatures during each 24-hour period. It is expected that these babies' temperatures will fluctuate by around one degree Celsius, and this is normal. Thus, analysis will explore whether fluctuations for each baby keep within this bound. A 95% confidence interval will be calculated around the mean of these fluctuations within each baby for each of the two incubators. Data from 36 babies would allow such a confidence interval to be calculated to within plus or minus 0.33 of a degree if the actual mean fluctuations are around one degree (*i.e.* as normally expected) and assuming a two-sided confidence interval.

Each patient will serve as their own control. The order of incubator type used for each of the two consecutive 24-hour periods of incubator care, and therefore which study arm the subject is recruited to, will be assigned randomly. A Microsoft Excel random number generation system will be used to generate random numbers with which the arm of the study which the subject is to enter will be assigned. Each assignment will be placed in an envelope attached to each CRF already numbered with a continuous series subject number.

Baseline demographic factors of the study subjects will be summarised. For continuous variables, such as weight, the mean, standard deviation, median and range will be presented. For categorical variables, such as gender, the proportion of subjects in each category will be presented.

All data will be analysed based on intention-to-treat. Statistical analysis will focus on babies' temperature fluctuations whilst in each of the two incubators. Graphical displays of these, as well as summary statistics such as the variance of temperature throughout the two 24-hour periods will be presented. A 95% confidence interval for the size of these temperature fluctuations for each incubator type will be calculated and this measure will be used to consider whether the mOm incubator works as well as the standard one in maintaining temperature control. Secondary outcome measures will be presented similarly.

Questionnaire data will be summarised to assess usability and acceptability of the mOm incubator to the clinical research team (staff).

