5. STUDY DESIGN

The study has a prospective, multi-centre, randomised controlled, cross-over design. There will be two arms to the research. The first arm will consist of mOm incubator

care for 24 hours, followed by a further 24 hours where the subject is transferred for care to a standard incubator. The second arm will consist of 24 hours care in a standard incubator followed by 24 hours care in a mOm incubator. The care of the baby (subject) is mostly unchanged from standard incubator care, but observations may be recorded more frequently (*i.e.* hourly) for incubator displayed temperatures and some other physiological measures of clinical stability than would normally be collected in routine care for this type of clinically stable baby of at least 30 weeks GA (normally every three hours) (See Table 1). No additional blood tests or any other invasive testing or monitoring are required. The clinical research team will have full control and responsibility for the baby's care, with the ability to withdraw the baby from the study at any time for any reason if they feel the baby is clinically unstable or is adversely affected by their environment. The order of incubator type in which the baby is cared for (*i.e.* which arm of the study) before being crossed over to the alternative incubator type will be assigned at random at the point of written consent being gained and the subject therefore having been officially recruited.

Babies that are considered clinically stable from a cardio-respiratory point of view but require at least 48 hours incubator care but not requiring additional humidification will be recruited to the study from the Neonatal Unit. In practice, this will mostly be babies weighing less than approximately 1400g at 30 weeks, although some term babies may also be eligible for the study if they are being nursed in an incubator for clinical reasons.

The aim is to collect 36 completed data sets for analysis; to achieve this approximately 40 babies will be recruited; recruitment will be stopped once 36 completed data sets are available. The target is to complete recruitment within a nine-month period.

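### Section 8 says the primary endpoint is compared between arms, but the arms are incubator orders; the within-baby mOm-minus-standard difference is not specified

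*Combined protocol and SAP*

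**What the plan says.** Section 5 defines the arms by sequence. The first arm is mOm care for 24 hours, "followed by a further 24 hours where the subject is transferred for care to a standard incubator". For the other arm: "The second arm will consist of 24 hours care in a standard incubator followed by 24 hours care in a mOm incubator". Section 6.2 refers back to that definition. Section 8 uses the word in the same sense, saying that the order of incubators, "and therefore which study arm the subject is recruited to, will be assigned randomly". No section uses the word to mean incubator type.

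Section 8 then states the comparison for the primary endpoint: "Variations from this endpoint will be analysed and compared statistically between the two arms of the study". This is the only sentence in the section that announces a statistical comparison.

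Other sentences in Section 8 work by incubator:
- "Each patient will serve as their own control".
- "A 95% confidence interval will be calculated around the mean of these fluctuations within each baby for each of the two incubators".
- "Statistical analysis will focus on babies' temperature fluctuations whilst in each of the two incubators".
- On the per-incubator interval: "this measure will be used to consider whether the mOm incubator works as well as the standard one in maintaining temperature control".

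Section 8 defines no mOm-minus-standard difference, no paired test or interval, no margin and no term for period or order.

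**The concern.** The trial asks whether mOm holds a baby's temperature as well as a standard incubator (Sections 2 and 3.1). A comparison between arms, taken at its word, sets babies who had mOm first against babies who had it second. Both groups had the same exposure to both devices. If the two periods are pooled within each baby, the contrast reflects sequence or carry-over effects and chance differences between two groups of babies. It carries no information on the device.

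Two misreadings could follow. An unremarkable arm contrast could be taken as support for the hypothesis in Section 2, although it would be expected even if mOm were clearly worse. A marked arm contrast could be reported as a device difference when it reflects order.

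**Working it through.** **Inputs.** From Section 8: 36 completed datasets, a two-sided 95% interval, a half-width of 0.33 °C, and mean fluctuation of about 1 °C. From Section 5: two orders, with both incubators used in each. Assumed, because the documents do not give them: SD of fluctuation 1 °C per incubator, 18 babies per order, within-baby correlation ρ of 0, 0.5 or 0.8, and no carry-over.

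**Step 1: the plan's own figure.** Half-width = 1.960 × SD/√n. With SD = 1 and n = 36 this is 1.960/6 = 0.327, which rounds to the stated 0.33. With 18 babies it would be 1.960/√18 = 0.46. The stated precision is therefore for one incubator using all 36 babies, and it implies SD of about 1 °C.

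**Step 2: what a comparison between arms estimates.** Let μ be the mean fluctuation in a standard incubator in period 1, d the mOm excess and π the period effect.

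| | Period 1 | Period 2 | Mean of both | Period 1 − period 2 |
|---|---|---|---|---|
| mOm first | μ + d | μ + π | μ + d/2 + π/2 | d − π |
| Standard first | μ | μ + d + π | μ + d/2 + π/2 | −d − π |
| Difference between arms | d | −d | 0 | 2d |

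- Pooling both periods: d cancels, whatever the SD or ρ.
- Comparing period differences between orders: the contrast is 2d, so half of it estimates d. This is the usual crossover estimator.
- Using period 1 only: the contrast is d, but the pairing is lost.

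Section 8 does not say which of these is meant.

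**Step 3: size.** Simulated proportion of trials giving a signal (200,000 trials per row). For the tests this means two-sided p < 0.05. For the separate intervals it means that the two 95% intervals do not overlap. That last criterion is my way of reading them, since the plan gives no rule.

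| d (°C) | ρ | Pooled, by arm | Period differences, by arm | Paired mOm − standard | Period 1 only, by arm | Separate intervals |
|---|---|---|---|---|---|---|
| 0.5 | 0 | 5% | 54% | 54% | 31% | 24% |
| 0.5 | 0.5 | 5% | 83% | 83% | 31% | 17% |
| 0.5 | 0.8 | 5% | >99% | >99% | 31% | 9% |
| 1.0 | 0 | 5% | 98% | 98% | 83% | 91% |
| 1.0 | 0.5 | 5% | >99% | >99% | 83% | 97% |
| 1.0 | 0.8 | 5% | >99% | >99% | 83% | 99% |

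At 0.5 °C, stronger within-baby correlation helps the paired contrast. It makes non-overlap of the separate intervals less likely, because their widths ignore the pairing.

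**Step 4: precision of the paired difference.** Half-width = 1.960 × √(2(1 − ρ))/√36 with SD 1, which is 0.46, 0.33 and 0.21 °C at ρ = 0, 0.5 and 0.8.

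**The case against.** The strongest reply is that the judgement on mOm does not rest on the arm contrast. Section 8 ties it to the 95% interval for each incubator, directs the analysis to fluctuations in each incubator, and makes each baby its own control. Sections 2 and 3.1 make the intended comparison clear, so the arms sentence may simply be loose wording for the two incubator conditions. Section 8 also calls the analysis largely descriptive and names no significance test. Cancellation needs a step that the plan never states, namely pooling the two periods before comparing arms.

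Much of this stands. A reader might infer that the device effect must cancel, or that the trial cannot detect a worse incubator. The documents do not support either. Comparing period differences between the same two arms recovers the effect, and the separate intervals fail to overlap in 91% to 99% of simulated trials at 1.0 °C.

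It does not remove the point. The arms are defined consistently as orders, so the literal sentence names the wrong groups. The own-control statement gives a principle without an estimator. The per-incubator intervals are never combined into a difference. Recovering the intended comparison is left to the analyst, who could choose a version that is blind to the device.

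**Conclusion.** The concern holds in limited form. The stated comparison for the primary endpoint is wrong as written, and no other part of Section 8 supplies a mOm-minus-standard contrast. The cancellation under pooling is algebraic and needs only the absence of carry-over. The plan as a whole can still show a large device effect through the per-incubator intervals, but it uses the crossover poorly. At a 0.5 °C excess those intervals separate in about 24%, 17% and 9% of trials (ρ = 0, 0.5, 0.8), against 54%, 83% and over 99% for the paired contrast. These percentages rest on SD 1 °C (inferred from the stated 0.33), 18 babies per order, the assumed range of ρ, no carry-over, and non-overlap as the way of reading two intervals. The correction should be made before the data are analysed.

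**What to change.** Make two changes in Section 8.

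1. In the primary-endpoint sentence, replace the reference to the two arms with: between the two incubator types (mOm versus standard) within each baby.
2. In the paragraph that says how mOm will be judged, report the mean within-baby mOm-minus-standard difference in fluctuation with its two-sided 95% confidence interval, and make that the basis for judging whether mOm works as well. The per-incubator intervals can stay as description. If the two orders end up unequal in size, averaging the difference within each order first, and then across the two orders, keeps a period effect out of the estimate.

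Keep any contrast between arms only as a labelled check for order effects, and state that a non-significant arm contrast is not evidence that mOm works as well.

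The cost is an edit to two sentences and one line on the order check. It needs no additional babies, measurements or procedures.

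### Intention-to-treat is declared, but 36 completed datasets are made the data for analysis, so whether a baby is analysed can depend on its temperature control; the direction of any bias is not established

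*Combined protocol and SAP*

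**What the plan says.** Section 8 gives the analysis population in one line, "All data will be analysed based on intention-to-treat", and does not define it further. The same paragraph directs the analysis at babies' "temperature fluctuations whilst in each of the two incubators". It plans a 95% confidence interval for the size of the fluctuations in each incubator type and adds that "this measure will be used to consider whether the mOm incubator works as well as the standard one".

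Other statements point to completers only. Section 5 says "The aim is to collect 36 completed data sets for analysis", expects to recruit about 40 babies to get them, and ends recruitment when 36 are in hand. Section 8 says "Thirty-six completed datasets are required for the analysis to be valid" and sets the standard: "A complete subject dataset will be deemed acceptable if 19 of the 24, once-hourly temperature observations have been recorded for each incubator type". Its reason is that "This degree of compliance was considered acceptable for analysis because it is still greater than the routine standard", which it describes as often three-hourly.

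The exit routes are in three places:
- Section 2.1.2 lets a baby in mOm be transferred to a standard incubator when there is concern about temperature stability or anything else. It also takes out of the study a baby who has an unforeseen serious adverse event while in mOm.
- Section 5 allows withdrawal for instability at any time, whichever incubator is in use.
- Section 6.4 does the same for serious events and protocol violations. It asks for reasons to be documented where possible.

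**The concern.** The two descriptions of the analysis set cannot both be followed once a baby has fewer than 19 readings in one incubator. Two analysts working from this plan could summarise different babies.

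The difference matters because the reason for a short period can be the outcome itself. The primary endpoint is variation in truncal temperature, and temperature concern is a named ground for leaving mOm early. If completers alone are analysed, such a baby drops out of the interval that supports the conclusion. Since recruitment runs on until 36 are complete, a baby who did complete in effect takes its place. What is at stake is a summary that makes one incubator look steadier than it was.

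**Working it through.** **1. The plan's own figures.** Half-width of the 95% interval = 1.96 × SD / √n. The SD is not stated; SD = 1 °C is the value that fits. With n = 36, 1.96 × 1 / 6 = 0.327, which rounds to the stated ±0.33 °C. The compliance figure is 19/24 = 79.2%, stated as 79%. Getting 36 complete from 40 recruited implies 4/40 = 10% incomplete.

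**2. Who is lost if only completers are analysed.** The 19-reading rule applies to each incubator.

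| Baby | Complete? | Effect of leaving it out |
|---|---|---|
| Leaves mOm for temperature concern before 19 readings | No | Could make mOm look steadier |
| mOm first, removed from the study during mOm, even with 19 or more mOm readings | No, no standard period | Could make mOm look steadier |
| Withdrawn for instability in the standard incubator before 19 readings there | No | Could make the standard incubator look steadier |
| Moved late, with 19 or more readings in each | Yes | None |

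**3. Size for the mOm mean.** Suppose k babies, each with mOm fluctuation d above the completers' mean, are left out and recruitment continues to 36 complete. Then N = 36 + k and the mOm mean is understated by k × d / N. The documents give no failure rate, so k and d are assumptions.

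| k of N | d = 0.5 °C | d = 1 °C | d = 2 °C |
|---|---|---|---|
| 1 of 37 | 0.014 | 0.027 | 0.054 |
| 2 of 38 | 0.026 | 0.053 | 0.105 |
| 4 of 40 | 0.050 | 0.100 | 0.200 |

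**4. Size for the comparison.** An excluded baby leaves both means. If a share s of its excess would also have appeared in the other incubator, the bias is (k_mOm − k_std) × d × (1 − s) / N. For d from 0.5 to 2 °C and N = 40:
- 4 v 0 losses: 0.05 to 0.20 with s = 0; 0.025 to 0.10 with s = 0.5; 0 with s = 1.
- 3 v 1, s = 0: 0.025 to 0.10.
- 2 v 2, s = 0: 0.
- 1 v 3, s = 0: −0.025 to −0.10.

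**5. Does adding partial data remove the bias?** Not reliably, because fluctuation measured over a short period tends to be low. This was simulated with normal hourly series and assumed lag-one correlations of 0, 0.5 and 0.8. The mean 5-reading SD is 95%, 82% and 66% of the 24-reading value, and the 2-reading SD is 80%, 60% and 43%. The range over 5 readings falls further, to 60%, 52% and 44%. At 66%, a failed baby needs about 1/0.66 = 1.5 times average variability just to leave the mean unchanged.

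Weighting matters too. Four failures with 5 readings each, beside 36 babies with 24, carry 20/884 = 2.3% of the weight if readings are pooled, but 4/40 = 10% if each baby counts equally.

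**6. What a count of early exits would show.** Exact 95% intervals: 1/37 = 2.7% (0.1 to 14.2); 2/38 = 5.3% (0.6 to 17.8); 4/40 = 10% (2.8 to 23.7).

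**The case against.** The strongest reply is that no section excludes or replaces anybody. Thirty-six can be read as a recruitment target and a minimum, with the intention-to-treat sentence governing. The 19-of-24 rule is justified against routine recording frequency, so it may be only a tolerance for missed observations. Section 6.4 does not discard data collected before withdrawal. This stands as far as it goes: exclusion is inferred. But both sections tie completeness to analysis, and no section says how a partial dataset is used.

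The second reply concerns size. Entry requires a prior day in a standard incubator, cardio-respiratory stability and no temperature instability, so early failures should be few. Treating all four planned losses as mOm thermal failures is an extreme case. This also stands, and it is why the result for one or two losses is given.

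The third is that nothing formal turns on the result: the plan says "Although data analysis will be largely descriptive" and sets no margin. That rules out a falsely crossed threshold. It does not make the choice of babies harmless, because the interval is still what the plan uses to judge mOm.

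A reader might infer more: that the plan removes mOm failures and is therefore tilted towards mOm. The documents do not support this. The mOm-specific wording of section 2.1.2 makes such a tilt plausible, but the completeness rule covers both incubators and withdrawal is possible from either. A reader might also infer that failures would be hidden. They would not: adverse and device events are recorded (sections 4.2.4, 6.2 and 7.1), and section 2.1.2 halts the study for a serious device event.

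**Conclusion.** The inconsistency is real and should be resolved before analysis. Under the natural reading, inclusion in the deciding measure can depend on the primary outcome. Neither the direction nor the size of the bias can be fixed from the documents.

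If all four implied losses were mOm failures with 0.5 to 2 °C excess, the mOm mean would be understated by 0.05 to 0.20 °C. The comparison would be biased by as much only if none of that excess were shared with the standard incubator. With one or two such losses the figure is 0.01 to 0.11 °C. All of these lie inside the stated ±0.33 °C. The likely harm is therefore a modest distortion of a descriptive comparison, with the failures reported elsewhere but not counted in the measure behind the conclusion.

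**What to change.** Reconcile section 5 with the two statements in section 8.

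1. Make the primary set all randomised babies with post-baseline truncal readings. Use readings taken in the incubator assigned for that period, and count each baby equally. Describe the set in those words instead of as unqualified intention-to-treat. Keep the plan's own fluctuation measure; this point does not call for a new one. Keep 36 completers as the recruitment target, and the 19-of-24 set as a paired sensitivity analysis.
2. Because short periods tend to show low fluctuation, report early exits beside the primary result and weigh them in the conclusion. Give the number and exact 95% interval of early moves or withdrawals for temperature concern in each incubator, among all babies who entered it. List removals for serious events separately.

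No clinical rule changes and no extra babies are needed, since non-completers are already recruited. The cost is rewording, one extra table and slightly more analysis work. The mOm result may look less favourable. The primary means will no longer rest on exactly the same babies, which weakens the own-control comparison there; the completer sensitivity analysis preserves it.

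### Section 8 asks whether each baby's temperature fluctuation stays within about one degree, but the measure feeding its conclusion is a confidence interval for the mean across 36 babies, which cannot answer that.

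*Combined protocol and SAP*

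**What the plan says.** All of this is in section 8 (Statistics and Data Analysis) of the combined protocol and SAP.

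- **The bound.** "It is expected that these babies' temperatures will fluctuate by around one degree Celsius, and this is normal". The normal limits given for truncal skin temperature, 36.5 to 37.5 °C, are also one degree apart.
- **The question.** "Thus, analysis will explore whether fluctuations for each baby keep within this bound".
- **The quantity estimated.** "A 95% confidence interval will be calculated around the mean of these fluctuations within each baby for each of the two incubators".
- **Its precision.** "Data from 36 babies would allow such a confidence interval to be calculated to within plus or minus 0.33 of a degree", on the condition "if the actual mean fluctuations are around one degree" and "assuming a two-sided confidence interval".
- **Its use.** Of the 95% interval for the size of fluctuations in each incubator type, the plan says "this measure will be used to consider whether the mOm incubator works as well as the standard one in maintaining temperature control".

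The section also calls the analysis largely descriptive, plans graphs and the variance of temperature over each 24-hour period, and says that variations in the primary endpoint will be compared statistically between arms. Section 7.1 lists hyperthermia and hypothermia among the adverse events to record. Nowhere does section 8 plan a number or percentage of babies outside the bound, or a paired count of them. It does not define fluctuation (range, standard deviation or departure from the limits), and it sets no margin or pass/fail rule for the interval.

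**The concern.** The question and the statistic have different targets. Whether each baby keeps within a bound is a matter of the distribution across babies, above all its upper tail. The interval concerns the centre of that distribution. It can lie entirely below one degree while several babies exceed one degree by a wide margin.

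An incubator may well fall short by losing control in some babies and not by a small equal shift in all of them. In that case the result that speaks most directly to the plan's own question is how many babies went out of bound in each incubator. As written, the report could conclude that mOm works as well, and imply that babies kept within the bound, from an interval that carries no such information.

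**Working it through.** **1. Which mean is meant?** The quoted sentence could be read as one interval per baby, so I reproduced the plan's precision figure first.

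- Inputs from section 8: n = 36, half-width 0.33, 95% two-sided, mean about 1. The SD is not stated.
- Formula: half-width = 1.96 × SD / √n.
- With SD = 1: 1.96 × 1 / 6 = 0.327, which matches 0.33. With t on 35 df, 2.030 / 6 = 0.338.
- Solving back from 0.33: SD = 0.33 × 6 / 1.96 = 1.01 (0.98 with t).

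The figure reproduces as the precision of a mean across 36 babies with an SD of about one degree. That settles the reading: one interval per incubator, across babies.

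**2. Can that interval lie below the bound while babies exceed it?** The values are illustrative and treat fluctuation as one number in degrees per baby: 32 babies at 0.7 and 4 (11%) at 2.0.

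- Mean = (32 × 0.7 + 4 × 2.0) / 36 = 30.4 / 36 = 0.844.
- SD = √[(4/36) × (32/36) × 1.3² × 36/35] = 0.414.
- Standard error = 0.414 / 6 = 0.069.
- 95% CI = 0.844 ± 2.030 × 0.069 = 0.70 to 0.985.

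The whole interval is below one degree, yet four babies swing by twice the bound. Varying the assumptions over baselines of 0.6 to 0.8 and failing values of 2.0 to 3.0, between 1 and 5 of 36 babies can fail with the whole interval at or below one degree.

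**3. What would a per-baby count give?** Exact (Clopper-Pearson) 95% limits with n = 36:

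| Babies exceeding | Percentage | 95% CI |
|---|---|---|
| 0 | 0% | 0 to 9.7% |
| 4 | 11.1% | 3.1 to 26.1% |
| 5 | 13.9% | 4.7 to 29.5% |

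For 0 of 36 the upper limit is 1 − 0.025^(1/36) = 0.097.

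**4. How many babies would exceed one degree with nothing wrong?** One degree is also the expected typical value. With mean 1, SD 1 (back-solved) and a gamma shape (assumed; at these values it is the exponential), the share above one degree is e^(−1) = 37%. A normal approximation gives 50%.

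**5. Would a paired test of exceedance be the better comparison?** I checked this by simulation under assumptions the plan does not give: n = 36, gamma fluctuations, correlation 0.5 between a baby's two periods, and each mOm baby having a 15% chance of an extra 2 °C. Over a range of means and SDs, including mean 1 and SD 1, the percentage of trials that miss the difference is:

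| Comparison of mOm with standard | Missed |
|---|---|
| CI for the within-baby mean difference includes zero | 36 to 72% |
| Wald CI for the paired difference in exceedance (> 1 °C) includes zero | 64 to 84% |
| Exact McNemar test on exceedance (> 1 °C) not significant | 80 to 92% |

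So at this bound a paired exceedance test is less sensitive than a within-baby comparison of fluctuation size. The count is needed because it answers the plan's question, not because it is more powerful.

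**The case against.** The strongest reply is that the plan is mostly descriptive and already looks at individual babies. It undertakes to explore each baby against the bound, to show graphs and variance, to compare variations between arms, and to record hypothermia and hyperthermia. With 36 babies, one that swings by an extra two degrees would be plain on a graph. This stands as far as visibility goes: a reader might infer that failing babies would be averaged out of sight, and the documents do not support that. What they lack is any stated per-baby result that reaches the conclusion about whether mOm works as well.

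A reader might also infer that the interval is a formal deciding test, for example that mOm passes if the upper limit is below one degree, and that the chance of this happening while many babies exceed one degree is an error to hold against 2.5%. Section 8 contains no such rule. Where the true mean is below one degree, an interval below one degree is a correct statement about the mean and not an error.

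Thirdly, a count needs a definition of fluctuation and a usable bound. The first is missing and the second is a typical value. Both parts of this stand, and they shape the fix. Finally, comparing average fluctuation does fit the primary objective in section 3.1, so the mean interval should be kept.

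**Conclusion.** The mismatch is real and should be corrected. Section 8 poses a per-baby question, and the only measure it names for the conclusion is an interval for a mean across 36 babies, which cannot answer it. That rests on the text and on the reproduced ±0.33, and it holds wherever the bound is set.

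Its size in this trial cannot be stated from the documents, because fluctuation is undefined and its SD is not given. The worked example (4 of 36 babies at 2.0 °C, interval 0.70 to 0.985) shows what is possible under assumed values, not what is likely. A reader might go on to infer that comparing exceedance counts would detect failures better than comparing means within baby. The simulation points the other way at one degree, so that claim should not be made.

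**What to change.** In section 8:

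- Define fluctuation as one value per baby per 24-hour period.
- Keep the 95% interval for the mean, described as a statement about average size only.
- Add to the measure used for the conclusion, for each incubator, the number and percentage of babies whose fluctuation exceeds the plan's own bound, with an exact 95% interval.
- Do not state that babies keep within the bound on the strength of the mean interval alone.
- Show descriptively the paired counts (exceeding in mOm only, standard only, both, neither) and the largest within-baby increases in mOm. Do not let a paired test of exceedance replace a within-baby comparison of fluctuation size.

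The cost is a few sentences and one table from data already collected, with no extra babies. There are two downsides. The intervals are wide: even 0 of 36 leaves just under 10% not excluded. And because one degree is also the expected value, a sizeable share of babies may exceed it in both incubators, so the mOm percentage means little unless read beside the standard one.
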